The study design is a 2 (Condition: ordinance, no ordinance) X 4 (Time: Baseline, 4-, 12-, 24month) quasi-experimental study. The primary hypothesis will be tested using traditional repeated measures modeling as well as growth curve modeling. The unit of analysis is the store, with Time a within-subjects factor and Condition a between-subjects factor. Condition, Time, and their interaction are modeled as fixed effects. The overall test of any difference by policy condition over time is the Time x Condition interaction, a 3 degree of freedom test. Planned contrasts will be used to examine specific hypotheses using single degree of freedom tests, assessing effects at 4-, 12- and 24-month follow-up. Because stores are not randomized to Condition, the statistical models will include a number of potential store-level covariates as additional fixed effects that have been identified from previous work. Covariance pattern modeling implemented by mixed model regression will be used to estimate the repeated measures model; this model allows residuals to correlate to account for the same stores being measured over time.

The repeated measures general linear mixed model includes time as a fixed effect and examines the effect of the policy on the outcome using the Time x Condition interaction. Using a series of planned contrasts, the effects of the intervention at each time point can be estimated (e.g., baseline to 4 months, baseline to 12 months, etc.). This model does not, however, explicitly model change over time. To examine change over time and how this relates to condition, we will augment these analyses with a series of conditional, multilevel models of change (i.e., growth curve models). These models examine inter-individual differences in intra-individual change by fitting a trajectory, with an intercept and slope, to each store. The intercept and slope can be regressed on predictors and covariates of interest.

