We will test Aim 1 (to assess changes in food availability pre- vs. post-policy implementation, as well as changes in food price, quality, promotion, and placement) by regressing each outcome variable separately on Time, Condition, and the Time x Condition interaction, as well as a number of potential covariates (store characteristics [e.g., type of store, size, customer base, store owner characteristics] and neighborhood characteristics [e.g., race/ethnicity, household income, poverty, education, employment]). The 3 df Time x Condition interaction is the overall test of the hypothesis; we hypothesize that this estimate will be significantly different from zero. We will conduct a set of single df planned contrasts to isolate effects. Controlling for any baseline differences, we will test differences between Condition (Policy vs. no Policy) at 4-, 12-, and 24-months post policy change. We hypothesize that stores in Minneapolis will show significantly

higher healthy food availability scores at all 3 time points. We will supplement these analyses using growth curve modeling. We will fit individual lines to each store's 4 waves of healthy food availability scores, and regress these intercepts and slopes on Condition and the potential covariates. We hypothesize stores in Minneapolis will show no baseline differences and have significantly larger positive slopes for healthy food availability outcomes over time. We will use growth mixture modeling⁽³⁴⁾ to examine policy compliance. Growth mixture modeling relaxes the assumption of population homogeneity and tests the presence of heterogeneity in trajectories. These models will identify subgroups of stores that exhibit similar compliance trajectories over time. After determining the optimal number of mixtures (subgroups), we will regress mixture on Condition (Minneapolis vs. St. Paul) and covariates. It is hypothesized that there will be a number of subgroups (e.g., immediate compliers, delayed compliers, non-compliers), Minneapolis stores will be more likely to be in a compliant subgroup (vs. a noncompliant subgroup), and various store and neighborhood characteristics will be associated with subgroup.

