We will test Aims 2 (assess changes in nutritional quality of purchases) and 3 (assess changes in home food availability among households that shop at small and non traditional, urban food stores) using similar models. For Aim 2, the data are repeated cross-sections (rather than true panel or longitudinal data) of small store consumers. Although individual change cannot be examined, we will assess aggregate change attributable to the policy change. Each nutritional quality measure (i.e., energy density, calories) will be regressed on Time, Condition, and the Time x Condition interaction, as well as a number of individual-level covariates. We hypothesize that the interaction will be significant, with purchases made in Minneapolis stores showing significantly lower energy density and calories at 4-, 12-, and 24-months post policy. For Aim 3, the data are true longitudinal data of households that frequently shop at small and non-traditional, urban food stores. This uses an identical repeated measures model as Aim 1, now with household as the unit of analysis. We will regress each food availability outcome variable separately on Time, Condition, and the Time x Condition interaction, as well as a number of household-level covariates. We hypothesize that the interaction will be significant, with households in Minneapolis showing significantly higher availability of healthy food and significantly lower availability of unhealthy food at 4-, 12-, and 24months post policy.

Analyses will be conducted with SAS or MPlus^(35, 36) Covariance pattern and growth curve models will be estimated using the SAS v9.3 MIXED procedure, which can estimate a large number of models, including general linear mixed models designed to analyze repeated measures and multilevel change. This procedure has built-in statements for specific planned contrasts. Growth mixture models will be estimated using MPlus v7.⁽³⁶⁾

Sample Size Considerations

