Because this is a study of a natural experiment, the number of available stores is not controllable. Based on estimates using our inclusion criteria, we expect to have 208 stores at baseline. Using means and variances from a recent study evaluating effects of WIC revisions on HFS scores⁽³⁷⁾ and setting alpha=0.05 (two-tailed) and power=0.80, we will be able to detect a difference in HFS score of approximately 2.2 points at any one time point. This is approximately 0.4 SD units and is much less than the difference found by Andreyeva and colleagues of approximately 4 points on the HFS score.⁽³⁷⁾ Even with substantially smaller sample sizes (i.e., <120 stores), we would have sufficient power to detect effect sizes on this order. Factoring in 20% attrition, the detectable effect increases

to approximately 2.4 units. Actual detectable effects will be much smaller given the additional power due to having multiple rounds of data and including covariates. Sample size calculations were also estimated for aims 2 and 3, also setting alpha=0.05 (two-tailed), and power=0.80. For aim 2, using variance estimates from Borradaile et al,⁽²⁸⁾ 424 intercept surveys at four rounds will allow us to detect a 50-calorie difference (a very small effect size) between conditions over time. For aim 3, 68 households will allow us to detect a 3-point difference (a small effect size) in fruit and vegetable availability and a 4-point difference in obesogenic home food score (also a small effect; variance estimates from Fulkerson et al⁽³⁸⁾, factoring in 20% attrition.

Quality Control

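### Aim 3 calls the differences detectable with 68 households small effects, and the sample size does not support that label

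*Combined protocol and SAP*

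**What the plan says.** Sample Size Considerations (section VI) sets two-sided alpha 0.05 and power 0.80 and states that "68 households will allow us to detect a 3-point difference (a small effect size) in fruit and vegetable availability", and likewise a "4-point difference in obesogenic home food score (also a small effect". The variances come from a cited validation study, and 20% attrition is factored in. Study Population (section IV, Home Food Inventory) gives 68 as the anticipated enrolment. For Aim 3 the plan gives no SD, no difference in SD units, no split between Minneapolis and St. Paul, no within-household correlation, no named contrast and no definition of small.

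The same section is more explicit for Aim 1. With 208 stores it gives 2.2 points at any one time point and adds "This is approximately 0.4 SD units". After 20% attrition the figure is about 2.4 points.

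Analyses That Will Be Performed (section VI) describes the tests. The overall one is a 3-df interaction: "The overall test of any difference by policy condition over time is the Time x Condition interaction, a 3 degree of freedom test". Beyond that, "Planned contrasts will be used to examine specific hypotheses using single degree of freedom tests, assessing effects at 4-, 12- and 24-month follow-up", and "the effects of the intervention at each time point can be estimated (e.g., baseline to 4 months, baseline to 12 months, etc". For Aim 1 it adds "Controlling for any baseline differences, we will test differences between Condition (Policy vs. no Policy) at 4-, 12-, and 24-months post policy change". Of Aim 3 it says "This uses an identical repeated measures model as Aim 1, now with household as the unit of analysis", with household-level covariates.

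**The concern.** Aim 3 uses the Aim 1 model with about a third as many units. The plan puts 208 stores at about 0.4 SD without calling that small, then calls what 68 households can detect small. In SD units, the detectable difference depends on the number of units, the split, the correlation and the contrast, and not on the outcome's SD. The label can therefore be examined even though the SDs are missing.

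Home food availability is one of three specific aims, with significant differences hypothesised at all three follow-ups. A reader who takes the label at face value would believe that small household changes are detectable with 80% power, and could read a non-significant Aim 3 result as evidence against them.

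**Working it through.** **Inputs from the plan.** Two-sided alpha 0.05; power 0.80; 68 households; 20% attrition, so 68 × 0.8 = 54.4, about 54.

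**Assumptions, because the plan is silent.** Equal split (27 per city, the most favourable for a comparison of two means); equal correlation r between waves, 0.5 to 0.8.

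**Formula.** Detectable difference in SD units ≈ (1.960 + 0.842) × √(1/n₁ + 1/n₂) × f. The results below use the noncentral t, which is slightly larger. The factor f is 1 for one unadjusted wave, √(2(1 − r)) for change from baseline to one wave, and √(1 − r²) for one wave with baseline as covariate.

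**Reproducing the plan's Aim 1 figure.** With 104 stores per city, 2.802 × √(2/104) = 0.389, or 0.390 with the noncentral t, against the stated value of about 0.4. With 83 per city the result is 0.437. At an SD of 2.2/0.4 = 5.5 this is 0.437 × 5.5 = 2.40 points, against the stated value of about 2.4. Aim 1 thus reproduces as an unadjusted comparison at one wave. For the same contrast, correlation and attrition, 68 households detect about √(208/68) = 1.75 times the Aim 1 value in SD units.

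**Aim 3, 27 complete households per city.** √(2/27) = 0.272 and 2.802 × 0.272 = 0.76, or 0.78 with the noncentral t.

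| Single-wave contrast | r = 0.5 | r = 0.7 | r = 0.8 |
|---|---|---|---|
| Unadjusted | 0.78 | 0.78 | 0.78 |
| Change from baseline | 0.78 | 0.60 | 0.49 |
| Baseline as covariate | 0.67 | 0.55 | 0.47 |

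The range is 0.47 to 0.78 SD. With all 68 retained it is 0.41 to 0.69; with a 36/18 split of 54 it is 0.49 to 0.82.

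**Closer to the planned mixed model.** Assume 34 households per city at baseline, then 32, 29 and 27, using all observed data (52 df). Change from baseline then detects 0.71 to 0.75 SD across the three waves at r = 0.5 and 0.45 to 0.48 at r = 0.8. With the baseline difference set to zero the figures are 0.62 to 0.67 and 0.43 to 0.46. If covariates explain a further 30% of variance, multiply by √0.7 = 0.837: the lowest is 0.428 × 0.837 = 0.36 and the highest 0.750 × 0.837 = 0.63.

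**Other readings, 54 complete households.** The 3-df test with an equal effect at all follow-ups detects 0.47 to 0.74 SD. The mean of three follow-ups with baseline as covariate, which the plan does not list, has f = √((1 + 2r)/3 − r²) and detects 0.37 SD at r = 0.8. At r = 0.9, the two baseline-adjusted single-wave contrasts detect 0.34 to 0.35 SD.

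**If small means 0.2 SD (assumption).** Power is 11% for one unadjusted wave and 22% with baseline as covariate at r = 0.8, both with 27 per city. It is 29 to 35% at r = 0.8 with partly observed households and the 30% covariates. The half-width of the 95% CI runs from 2.007 × 0.272 = 0.55 SD (unadjusted) down to 0.25 SD (the most favourable of these cases). With 27 per city and no further covariates, 80% power at 0.2 SD needs 1 − r² = (0.2/0.777)² = 0.066, so r of about 0.97; change from baseline gives the same to two decimals.

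**The case against.** The strongest reply is that no arithmetic error is shown. The 3 and 4 points rest on cited variances that cannot be seen here, and small is undefined, so the 0.2 SD benchmark is the reviewer's. That is correct. A reader might infer that the 3- and 4-point figures are wrong, or that the plan contradicts itself. The documents support neither; they show a label without support.

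A second reply is that 0.47 to 0.78 SD is not the range for the planned analysis. It leaves out partly observed households and household-level covariates, and for Aim 1 the plan itself notes that repeated rounds and covariates reduce the detectable effect. This also stands, and it is why the lower figures of 0.36 to 0.63 SD are given beside it. A reader might take 11 to 22% power, or ±0.33 to ±0.55 SD, as the range for the planned model; both come from complete households without further covariates and are too narrow.

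Third, the powered contrast is not named for Aim 3, and the correlation range is assumed. An averaged contrast or a correlation of 0.9 brings the figure to roughly 0.34 to 0.37 SD. That widens the range, but still does not reach 0.2 SD.

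Finally, the consequence is limited. The planned estimates and intervals will show the precision, and nothing in the plan says that a non-significant Aim 3 result will be read as no effect.

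**Conclusion.** The point holds as a matter of reporting: the plan claims 80% power for small effects in Aim 3, and the stated sample size does not support that description. The assumptions are an equal split and correlation 0.5 to 0.8, and for the lower figures also an assumed dropout pattern and 30% of variance explained by covariates. On these, the listed single-wave contrasts detect about 0.47 to 0.78 SD with complete households, and the baseline-adjusted forms about 0.36 to 0.63 SD in the more favourable analysis. The 0.2 SD benchmark is a further assumption; under it, power is about 11 to 35% and a null estimate would not exclude 0.2 SD. This is worth fixing. Confidence is medium, because the split, the correlation, the contrast and the meaning of small are all missing from the plan.

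**What to change.** Delete both small-effect labels. Restate the Aim 3 sensitivity from the authors' own inputs: the SD of each outcome, the 3- and 4-point differences in SD units, the number of households per city after attrition, the within-household correlation, and the contrast that was powered. Add that Aim 3 results will be reported as estimates with 95% CIs, and that a non-significant result will be interpreted from the effects its interval does and does not exclude.

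If the inputs cannot be recovered, delete the labels and give a detectable range in SD units only with every assumption shown (split, correlation, attrition, covariates, contrast). Do not insert 0.47 to 0.78 SD as a default. If the authors' inputs do support a small effect under a stated definition, supplying them settles the point.

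The cost is a less favourable stated sensitivity. Household enrolment took place at baseline only, so the sample cannot change. Model, contrasts and data collection are also unaffected.
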